19	BMI	Body Mass Index
20	LAAO	Left Atrial Appendage Occlusion

Summary of the Trial Protocol

Test Name	Evaluation of the Safety and Efficacy of Catheter Ablation After Left Atrial Appendage Occlusion with the WATCHMAN FLX Device
Sponsor	Department of Cardiology, Affiliated Hospital of Nantong University
Principal Investigator	[name]
Purpose of the test	
1. Main Purpose: To evaluate the safety and efficacy of catheter ablation performed one month after WATCHMAN FLX left atrial appendage occlusion (LAAO) in patients with non-valvular atrial fibrillation(AF).
 
2. Secondary Purpose: To investigate the impact of a two-surgery sequential treatment regimen on the recurrence rate of atrial fibrillation, the incidence of stroke, and the quality of life of patients, and to provide evidence-based support for decision-making in the clinical application of combined therapy.

Trial Population	Patients diagnosed with non-valvular AF who are scheduled to undergo sequential LAAO using the WATCHMAN FLX device and catheter-based ablation.
Trial Design	
This study is a prospective, single-arm, multicenter clinical trial designed to evaluate the safety and efficacy of catheter ablation performed one month after LAAO with the WATCHMAN FLX device. Approximately 210 patients with non-valvular AF who meet the indications for both transcatheter LAAO and catheter ablation will be enrolled across 10 research centers in China. The study procedures are outlined as follows: :
 
 Patient Screening and Enrollment: Eligible patients will undergo elective LAAO with the WATCHMAN FLX device (first procedure) after signing the informed consent form (ICF). Postoperative Management: Following the LAAO with the WATCHMAN FLX device, patients will undergo standard anticoagulation therapy for one month. If transesophageal echocardiography (TEE) reveals no device-related thrombosis (DRT) or residual flow >5 mm, the patient will undergo catheter ablation for atrial fibrillation (second procedure) one month after the initial LAAO.

	
3. Follow-up: Baseline patient data will be collected prior to the first procedure. Follow-up visits will occur within 7 days post-LAAO or at discharge, and at 1 month (i.e., time of the second procedure), 3 months, and 12 months post-procedure. Follow-up will focus on device endothelialization at 12 months, recurrence of atrial fibrillation, and occurrence of related complications.
 
Postoperative Medication Management Strategy:
 
Patients will receive anticoagulation therapy for 1 month following LAAO with the WATCHMAN FLX device. If no thrombosis or significant residual flow is detected, catheter ablation for atrial fibrillation will be performed. After the ablation procedure, anticoagulation therapy will be continued for an additional 2 months. Antiarrhythmic drugs (AADs) may be used within 90 days post-ablation in accordance with AF management guidelines.

Primary endpoint	The success rate of complete left atrial appendage (LAA) closure within 12 months following LAAO with the WATCHMAN FLX device, as assessed by LAA computed tomography angiography (CTA).
Secondary endpoint	
Safety Endpoints:
 
Incidence of procedure-related complications and adverse events within 30 days after LAAO and radiofrequency ablation, including rates of pericardial effusion, access site complications, vascular complications, and infections. The incidence of procedure-related complications and adverse events within 12 months following LAAO and radiofrequency ablation will be evaluated. These include major bleeding events (defined as those requiring blood transfusion or surgical intervention), cardiac tamponade, systemic embolism (including ischemic stroke and other embolic events), device-related thrombosis (DRT), new or enlarged peri-device leak (PDL, defined as >5 mm), acute postoperative left heart failure, and rehospitalization.
 
Efficacy Endpoints:
 
 1. Treatment success rate within 3 months after radiofrequency ablation (Early recurrence): No recurrence of atrial arrhythmias ≥ 30 seconds. 2. Treatment success rate between 4 to 12 months after ablation (Late recurrence): No recurrence of atrial arrhythmias ≥ 30 seconds during this period. 3. Incidence of stroke within 12 months following LAAO: No occurrence of stroke.

	
4. Quality of life improvement at 12 months measured by the Atrial Fibrillation Effect on Quality-of-Life (AFEQT) questionnaire: Improvement in quality-of-life score from baseline to 12 months following index ablation or AAD treatment, with a possible score range of 20 to 140 (higher scores indicate worse outcomes).

Entry Criteria	
 1) Age ≥ 18 years with a diagnosis of nonvalvular AF; 2) Eligible for indications for treatment with WATCHMAN FLX LAAO and transcatheter atrial fibrillation ablation; 3) Preoperative imaging evaluation showed that the LAA anatomy was suitable for WATCHMAN FLX device implantation; 4) Patients agreed to participate in the study and signed an ICF.
Exclusion criteria	
Patients meeting any of the following criteria were not eligible for this study:
 
 1) Presence of valvular heart disease or other structural heart disease that causes atrial fibrillation; 2) Preoperative detection of LAA thrombus or acute thrombotic event; 3) The patient has a severe bleeding tendency or a recent major bleeding event (e.g. gastrointestinal hemorrhage, cerebral hemorrhage, etc.); 4) Patients who are unable to complete postoperative follow-up (e.g. life expectancy less than 1 year or poor compliance); 5) Other serious diseases (e.g. liver and kidney failure, active infections, etc.) detected on preoperative examination; 6) Women who are pregnant or breastfeeding.
statistical analysis	
1. Sample size calculation:
 
The sample size was calculated based on the primary endpoint. The primary endpoint of this study was “12-month rate of complete closure of the block after WATCHMAN FLX LAAO (CT assessment).” Hypothesized target incidence $P_0 = 74.3\%$ and test incidence $P_1 = 84.3\%$. The significance level $\alpha = 0.05$ (one-sided) and test efficacy $1 - \beta = 80\%$ were calculated to be 200 cases able to fulfill the hypothesis test. Considering the 5% shedding rate, the total sample size was 210 cases.
 
2. Descriptive Statistics:
 
Patient baseline characteristics (e.g. age, sex, history of AF) were expressed as mean \pm standard deviation or median (quartiles) for continuous variables,

	
and frequency and percentage for categorical variables.
 
3. Primary endpoint analysis:
 
The 12-month complete closure rate of the WATCHMAN FLX device was characterized by point estimates and their 95% confidence intervals and tested against the target value of $P_0 = 74.3\%$ in a one-sample hypothesis test ($\alpha = 0.05$).
 
4. Secondary endpoint analysis:
 
Safety events (e.g. pericardial effusion, puncture site complications) were described by incidence rates and their 95% confidence intervals were calculated. Changes in quality of life were analyzed by chi-square test or paired t-test for time effects.

--	---

Text of the Trial Protocol

1. Study information

Name of Sponsor: Affiliated Hospital of Nantong University

Principal Investigator: [name]

2. Background

Atrial fibrillation (AF) is one of the most common persistent arrhythmias in clinical practice, and its prevalence increases significantly with age, posing a serious threat to public health globally [1]. One of the most serious complications in patients with AF is thromboembolic events, especially cardioembolic stroke. Cardioembolic strokes due to AF account for 20-30% of all strokes and are associated with significantly higher rates of mortality and disability in post-stroke patients [2]. Studies have shown that approximately 90% of blood clots in patients with nonvalvular atrial fibrillation originate from the left atrial appendage (LAA) [3]; therefore, preventing stroke by isolating the LAA from the atria has become an important strategy in the management of patients with AF, a surgical procedure known as left atrial appendage occlusion (LAAO) [4]. Furthermore, international and national guidelines for arrhythmia management state that rhythm control and stroke prevention are equally important in patients with AF. Although LAAO has been shown to be effective in reducing the risk of stroke associated with AF [5], it does not address the arrhythmia of the patient. In contrast, catheter ablation is one of the most effective treatments for rhythm control, and has been shown in several randomized controlled trials (RCTs) to significantly improve sinus rhythm maintenance and quality of life in patients with AF [6-9]. These studies have shown that catheter ablation is the method of choice for rhythm control in patients with paroxysmal AF, with better long-term outcomes compared with pharmacologic therapy. To address rhythm control and stroke prevention in patients with AF in an integrated manner, combining catheter ablation and LAAO is a feasible and promising therapeutic strategy. Catheter ablation aims to restore sinus rhythm by intervening in the triggering mechanism of AF, whereas LAAO reduces the risk of stroke by isolating the main site of thrombus formation. The combination of the two surgical approaches not only improves the maintenance of sinus rhythm in patients, but also significantly reduces the risk of stroke and all-cause mortality [10].

Currently, the use of combinations of these two procedures is increasing in clinical practice. Some studies and expert consensus suggest that the goal of integrated therapy can be achieved by "one-stop surgery" (performing both catheter ablation and LAAO in a single operation) or staged surgery (performing one procedure before the other) [11].

Evaluation of the Safety and Efficacy of Catheter Ablation Following Left Atrial Appendage Occlusion Using the WATCHMAN FLX Device
However, there are no uniform conclusions regarding the optimal sequence of procedures. Some studies have shown that concurrent "one-stop" surgery may reduce hospitalization time, surgical risk, and patient financial burden [12], while staged surgery allows physicians to better assess outcomes after the initial surgery and reduces the overall surgical risk to the patient [13].

The 2021 expert consensus on the management of atrial fibrillation in China made a class IIb recommendation for "one-stop surgery", suggesting that for some patients with nonvalvular AF who have indications for both catheter ablation and LAAO, it is reasonable to perform LAAO at the same time as catheter ablation. Nevertheless, there is a lack of trials to validate the advantages and disadvantages of different procedural sequences in terms of safety and efficacy.

Therefore, the aim of this study was to evaluate the safety and efficacy of transcatheter AF ablation 1 month after WATCHMAN FLX LAAO, to provide an evidence-based medical rationale for optimizing the comprehensive management of patients with AF, and to further explore the optimal combined strategy of the two surgical approaches in patients with nonvalvular AF.

3. Study design

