3.2.2 Exclusion criteria

Patients meeting any of the following criteria were not eligible for this study:

- 1) Presence of valvular heart disease or other structural heart disease that causes atrial fibrillation;
- 2) Preoperative detection of LAA thrombus or acute thrombotic event;
- 3) The patient has a severe bleeding tendency or a recent major bleeding event (e.g. gastrointestinal hemorrhage, cerebral hemorrhage, etc.);
- 4) Patients who are unable to complete postoperative follow-up (e.g. life expectancy less than 1 year or poor compliance);
- 5) Other serious diseases (e.g. liver and kidney failure, active infections, etc.) detected on preoperative examination;
- 6) Women who are pregnant or breastfeeding.

4. Study process

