8.4 Expected adverse reactions

The following anticipated complications may result from the occluder or antithrombotic medications:

1, Device related thrombosis 2, Ischemic stroke 3, Pericardial effusion 4, Hemorrhagic stroke 5, Cardiac tamponade 6, Nuisance bleeding 7, Hemorrhage 8, Death

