8.6 Security incident audits

To ensure the safety of subjects during the conduct of the study, the safety of the clinical trial will be assessed by analyzing and reviewing major safety events at regular intervals during the conduct of the study. Given that all-cause mortality, ischemic stroke, and major bleeding events are the most relevant adverse events related to device or procedure safety, the focus will be on monitoring and evaluating these three types of events. Once the number of subjects with safety events reaches or exceeds the expected number of cases, safety investigations and appropriate treatment measures will be triggered.

References:

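### The 12-month safety endpoint counts a bleed as major only if it needed transfusion or surgery, so a fatal or intracranial bleed managed with neither is left out, and all-cause death is not named

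*Protocol*

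**What the plan says.** The safety endpoints are defined only in the Summary of the Trial Protocol, Secondary endpoint row; the body has no endpoint section. The 12-month part opens with a general sentence: "The incidence of procedure-related complications and adverse events within 12 months following LAAO and radiofrequency ablation will be evaluated". A list of included events follows. Its bleeding component is "major bleeding events (defined as those requiring blood transfusion or surgical intervention". Its stroke-related component is "systemic embolism (including ischemic stroke and other embolic events". It also names cardiac tamponade, device-related thrombosis and peri-device leak, and ends with "acute postoperative left heart failure, and rehospitalization". Death and haemorrhagic stroke are not named.

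Other parts of the protocol bear on the same events:

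- Exclusion criterion 3 (Summary and section 3.2.2) bars patients with "a recent major bleeding event (e.g. gastrointestinal hemorrhage, cerebral hemorrhage, etc", with no condition on how the bleed was treated.
- Section 8.4 lists anticipated complications, including "4, Hemorrhagic stroke 5, Cardiac tamponade", and ends its list with death.
- Section 8.6 explains the choice of monitored events: "Given that all-cause mortality, ischemic stroke, and major bleeding events are the most relevant adverse events".
- Section 8.2.1 makes an event leading to death a serious adverse event.
- Efficacy endpoint 3 counts stroke within 12 months of LAAO and does not specify a type.

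**The concern.** Safety of ablation after LAAO is part of the main purpose, and patients are anticoagulated for one month after LAAO and two more after ablation. Major bleeding is therefore one of the rates readers will look at first. A definition based only on treatment received leaves out bleeds that are grave because of their site or outcome. Examples are an intracranial bleed managed conservatively, or a bleed that kills before either treatment can be given. The omission works in one direction only, because it can lower the reported rate and never raise it.

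The protocol itself treats these events as important. It uses cerebral haemorrhage as an example of a major bleed at entry, expects haemorrhagic stroke and death, and ranks all-cause mortality among its key safety events. The endpoint list does not carry this through. In a single-arm study of 210 patients, where safety is described by rates with confidence intervals, a few unlabelled events can change how the result reads.

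**Working it through.** The protocol states no expected safety rate, margin or safety sample size, so there is no figure to reproduce. The check is a comparison of texts, followed by a scale for the possible effect.

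**Step 1. Where each event lands in the 12-month safety list**

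| Event on study | Major bleeding | Systemic embolism | Other named place |
|---|---|---|---|
| Bleed needing transfusion or surgery | Yes | No | – |
| Intracranial bleed, neither treatment, patient survives | No | No (ischaemic and embolic events only) | Efficacy endpoint 3 if classed as stroke; rehospitalization if readmitted |
| Fatal non-cerebral bleed, neither treatment (e.g. gastrointestinal) | No | No | None that records it as a bleed; serious adverse event (8.2.1) and mortality monitoring (8.6) |
| Death from another cause | – | – | Not named; serious adverse event and mortality monitoring as above |

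A bleed into the pericardium could be listed as tamponade, so the gap concerns other sites.

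**Step 2. Does the open list cure this?** The general sentence and the word introducing the list leave the set of events open, so an unnamed event may still be reported as an adverse event. The bleeding component, however, carries its own closed definition in brackets. An open list does not widen that definition, and the reported major-bleeding rate will follow it.

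**Step 3. Consistency with the rest of the protocol.** Under exclusion criterion 3, a recent cerebral haemorrhage keeps a patient out as a major bleed. Under the endpoint, the same haemorrhage after enrolment is a major bleed only if transfused or operated on. Section 8.6 monitors major bleeding but neither defines it nor refers to the Summary, so it is not settled which meaning applies there.

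**Step 4. Scale.** With N = 210, each uncounted patient lowers the rate by 1/210 = 0.48 percentage points. Exact (Clopper-Pearson) 95% intervals for the rate of uncounted patients, for hypothetical counts:

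- 2/210 = 1.0% (0.1 to 3.4)
- 4/210 = 1.9% (0.5 to 4.8)
- 6/210 = 2.9% (1.1 to 6.1)

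As a range under assumptions the protocol does not supply, take a true major-bleeding rate of 3 to 5% and 10 to 30% of those bleeds managed with neither treatment:

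- Low end: 3% × 10% = 0.3 percentage points, or 210 × 0.003 = 0.6 patients.
- High end: 5% × 30% = 1.5 percentage points, or 210 × 0.015 = 3.2 patients.

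These figures show scale only and do not estimate what will happen.

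**The case against.** The strongest reply is that nothing is lost to the trial. The 12-month endpoint covers adverse events generally, and section 8.1.1 counts them whether or not the device caused them. Deaths are serious adverse events and are monitored under section 8.6, and a haemorrhagic stroke can count under efficacy endpoint 3. The exclusion criterion describes bleeding history for eligibility and is not an outcome definition. Safety is descriptive (section 6.2.2), so no test or margin changes. Most of this stands, and it limits the point to what is labelled and reported as major bleeding and as death. It does not widen the bracketed definition. A sympathetic reader could say that a patient who bled to death required transfusion even if none was given. That might rescue some fatal bleeds, at each site's discretion, but not an intracranial bleed for which neither treatment was needed.

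Three stronger readings are tempting and are not supported:

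- **Death is excluded from the safety endpoint.** It is unnamed in an open list. No closed composite is defined from which it would be missing.
- **The narrow definition governs the section 8.6 monitoring.** That section does not import it; the meaning there is simply unstated.
- **Rehospitalization takes in the planned ablation admission, so its rate approaches 100%.** The design does say "the patient will undergo catheter ablation for atrial fibrillation (second procedure) one month after the initial LAAO", and the section 4.1 schedule has a separate post-ablation discharge. But the word sits under complications and adverse events, and section 8.1.1 requires an adverse or worsening medical condition, which a scheduled procedure is not. All that can be said is that the planned admission is not expressly set aside.

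**Conclusion.** The point holds as a defect of endpoint definition. The protocol fixes a closed definition of major bleeding that leaves out fatal and intracranial bleeds managed without transfusion or surgery, which is at odds with its own use of the term at entry. It also does not name all-cause death among the 12-month safety events, although section 8.6 ranks it among the most relevant. Applied as written, the definition biases the reported major-bleeding rate downward whenever such a bleed occurs.

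The size cannot be derived from the document. The illustrative 0.3 to 1.5 percentage points rests wholly on assumed rates. What is affected is a descriptive secondary rate and not a trial decision: no safety hypothesis, margin or sample size depends on it. The correction is still worth making, because safety is in the main purpose and the protocol itself has fixed the wording.

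**What to change.** In the 12-month safety endpoint:

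1. Define major bleeding as bleeding that is fatal, or intracranial, or needs transfusion or surgical intervention.
2. State in section 8.6 that its monitoring of major bleeding uses this same definition.
3. Name all-cause death as a reported event, with its incidence and 95% CI.
4. As a minor clarification, state that the scheduled ablation admission does not count as rehospitalization.

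The cost is protocol and case report form wording, with the ethics committee approval that section 7.1 requires for any modification. No new data collection is needed, since these events are already recorded as adverse or serious adverse events. The downside is that the reported major-bleeding rate may be slightly less favourable.

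### Late rhythm success and AFEQT are timed from an ablation one month after LAAO, but the single one-year visit has no stated origin and, counted from LAAO, ends a month short

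*Protocol*

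**What the plan says.** **Endpoints.** The Protocol Summary uses two clocks.

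- Primary endpoint, counted from LAAO: "The success rate of complete left atrial appendage (LAA) closure within 12 months following LAAO with the WATCHMAN FLX device". Section 6.1 likewise describes a 12-month closure rate after LAAO, assessed by CT.
- Early rhythm success, counted from ablation: "Treatment success rate within 3 months after radiofrequency ablation (Early recurrence").
- Late rhythm success, counted from ablation: "Treatment success rate between 4 to 12 months after ablation (Late recurrence): No recurrence of atrial arrhythmias ≥ 30 seconds during this period".
- AFEQT: change from baseline to 12 months after the index ablation or antiarrhythmic drug treatment.

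**Interval between the procedures.** Under Trial Design in the Summary, if TEE is satisfactory, "the patient will undergo catheter ablation for atrial fibrillation (second procedure) one month after the initial LAAO".

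**Visits.** The Summary lists follow-up "at 1 month (i.e., time of the second procedure), 3 months, and 12 months post-procedure". The table in section 4.1 labels Visit 4 as one month after surgery, which is the ablation. Visits 6 and 7 are labelled three months and one year after surgery, without saying which of the two procedures is meant. Section 4.2.1 ends participation at one year of follow-up, again without an origin. No visit windows are given. In the section 4.1 table, CT is mandatory only at Visit 7, and AFEQT has no row at all.

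**The concern.** With two procedures a month apart, a single final visit cannot be at 12 months on both clocks. Whichever origin is used, one endpoint is defined over a period that the schedule does not match.

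The endpoints affected are not peripheral. Section 3.1 gives the safety and efficacy of the staged ablation as the main purpose, and recurrence and quality of life as part of the secondary purpose. A rate labelled as covering months 4 to 12 after ablation would, on the more natural reading of the visit table, rest on follow-up that stops near month 11. AFEQT would have no visit at its defined time.

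A statistical analysis plan can define analysis windows, but it cannot create a visit or extend participation. The point therefore belongs in the Protocol.

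**Working it through.** **Inputs**

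- Interval from LAAO to ablation: 1 month (Summary, Trial Design).
- Visit 6 at 3 months and Visit 7 at 12 months from an unnamed procedure (section 4.1).
- End of follow-up: 1 year, origin unnamed (section 4.2.1).
- Late-rhythm window: months 4 to 12 after ablation. AFEQT: 12 months after ablation or drug treatment. Closure: 12 months after LAAO (Summary).

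The Protocol gives no figure of its own to reproduce here.

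**Step 1. Which origin does the text support?**

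For LAAO:

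- The 1-month point in the follow-up series is the ablation itself, so it can only be counted from LAAO. The 3- and 12-month points belong to the same series.
- The only mandatory CT is at Visit 7, which suits a primary endpoint counted from LAAO.
- The Summary's medication section gives one month of anticoagulation after LAAO and then "After the ablation procedure, anticoagulation therapy will be continued for an additional 2 months". That makes 1 + 2 = 3 months after LAAO, which coincides with Visit 6 on the LAAO count.

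For ablation:

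- In the Summary's list, the 3- and 12-month points come directly after the mention of the second procedure.
- In section 4.1, Visits 6 and 7 follow Visit 5, whose label refers to the ablation.

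LAAO is better supported, but nowhere stated for Visits 6 and 7.

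**Step 2. Convert the visits.** Time from ablation = time from LAAO − 1 month.

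| Origin of Visits 6 and 7 | Visit | Months from LAAO | Months from ablation |
|---|---|---|---|
| LAAO | 6 | 3 | 3 − 1 = 2 |
| LAAO | 7 | 12 | 12 − 1 = 11 |
| Ablation | 6 | 3 + 1 = 4 | 3 |
| Ablation | 7 | 12 + 1 = 13 | 12 |

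**Step 3. Compare with the endpoint definitions.**

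- *LAAO origin.* Closure is met at 12 months. Follow-up ends 11 months after ablation, so 12 − 11 = 1 month of the late-rhythm window lies beyond it. If the window is months 3.0 to 12.0, that is 1/9 = 11.1%. If it is months 4.0 to 12.0, it is 1/8 = 12.5%. No scheduled visit reaches 12 months after ablation for AFEQT.
- *Ablation origin.* The rhythm window and the 12-month post-ablation point are met. The only required CT comes 13 months after LAAO, 1 month outside the primary endpoint's window.

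**Step 4. Can a bias in late success be computed?** It cannot. It would need the true recurrence rate, its shape over time and the chance of detecting a recurrence between visits. The only rhythm test in the section 4.1 table is a 12-lead ECG. On the LAAO origin, Visit 6 is at month 2 after ablation, before the late window opens, so Visit 7 supplies the one scheduled ECG within that window.

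**The case against.** The strongest reply is that the origin can be inferred. The 1-month label can only mean LAAO, the mandatory CT sits at Visit 7, and so the primary endpoint is safe. What remains is one month on secondary endpoints, which a reasonable visit window might absorb. Most of this stands. LAAO is the natural reading, and the 13-month CT deserves little weight. But accepting LAAO does not remove the mismatch. It places it on late rhythm success and AFEQT, and the Protocol states no window that would cover a month.

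Several stronger readings are tempting but not supported:

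- *That late success will be overstated by some number of percentage points.* Losing the last month can only hide recurrences that would otherwise have been found. With a 12-lead ECG as the only scheduled rhythm test, detection between visits depends on symptoms or unscheduled care. If recurrence is seen only on visit ECGs, the effect may be near zero.
- *That AFEQT is measured a month early.* The visit table has no AFEQT row, so its timing is unassigned rather than shown to be wrong. Its clock also names drug treatment as an alternative start.
- *That stroke is caught in the same conflict.* The endpoint is "Incidence of stroke within 12 months following LAAO". Both origins cover that period, and events can be cut by date.
- *That a month between the early and late windows belongs to neither.* Within 3 months followed by 4 to 12 months reads naturally as months 1–3 and then months 4–12, which are contiguous.
- *That early recurrence is lost because Visit 6 may fall 2 months after ablation.* A recurrence in month 3 can be reported and dated later.
- *That the 12-month safety window is in error.* Its wording, "within 12 months following LAAO and radiofrequency ablation", names both procedures, as does the 30-day window, and may well mean after each. Clarifying it would help, but it is not a contradiction.

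**Conclusion.** The mismatch is real and should be corrected. On the better-supported LAAO origin, stated follow-up ends about 11 months after ablation. About one month of the late-rhythm window, between 1/9 and 1/8 of it, is then not covered, and no visit exists at the 12-month post-ablation AFEQT point. On the less natural ablation origin, the required CT falls about a month outside the primary window instead.

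This rests on ablation taking place at the planned one month and on there being no visit window. A later ablation would widen the gap by the length of the delay. The calendar conclusion is firm. The effect on the reported late success rate is unknown and may be negligible, and no direction can be given for AFEQT. The primary analysis is not threatened if the final visit is counted from LAAO.

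**What to change.** State that Visits 6 and 7 and the one year of follow-up count from LAAO, and keep the required CT at 12 months after LAAO. Then choose one of the following.

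- **(a)** Define and report late rhythm success and AFEQT as running to the 12-month post-LAAO visit, about 11 months after ablation, and assign AFEQT to that visit in section 4.1. This changes wording and the visit table only. The cost is a reported post-ablation window about one month shorter.
- **(b)** Add one rhythm and AFEQT contact at 12 months after ablation, and extend the stated end of follow-up to match. The cost is one extra contact per patient, with participation running to about 13 months after LAAO.

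Under either option, assign each recurrence to the early or late period by its documented date. Stating the early/late boundary in days and the origin of the 12-month safety window are optional clarifications that could go in at the same time. Under section 7.1, either option needs ethics committee approval before it is implemented.
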